### *Methods*

Sixty patients following total knee arthroplasty will be monitored for up to 10 weeks during their outpatient physical therapy course. For the control group, 30 of these patients will undergo two to three weekly sessions with a physical therapist supplemented by unmonitored home-based exercises. The second group of 30 patients will fulfill their rehabilitation course with one to three sessions per week with a physical therapist and will use the interACTION home rehabilitation monitoring program to supplement these sessions. The patients in the interACTION group will use the device for the first two weeks of their rehabilitation in the clinic in order to become familiar with the device before home use. After the first two weeks the patient will be asked to take the device home and reduce their weekly outpatient visits by one visit per week. However, if the physical therapist feels it is best for the patient to deviate from the protocol, this is allowed. At the end of the 10-week rehabilitation course, rehabilitation compliance, costs, and patient outcomes will be analyzed for differences between the two groups.

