## **Methods**

For this randomized treatment study, we will recruit 60 patients that have undergone total knee arthroplasty (TKA) that are being referred for post-operative outpatient physical therapy. After obtaining informed consent, and upon successful

screening/recruitment, subjects will be randomly assigned to one of two groups:

1. Control Group: Rehabilitation performed by a physical therapist and supplemented with a home exercise program for a maximum of ten weeks. Therapy will consist of two to three visits per week as prescribed by the physical therapist and based on the best interest of the patient. Patients will record their performance of the prescribed home exercise programs on a paper-based exercise log on a daily basis.
2. InterACTION Intervention Group: Rehabilitation performed by a physical therapist and supplemented by use of interACTION for a maximum of ten weeks. This will include two to three visits per week for two weeks in which the patient will use interACTION during routine outpatient physical therapy sessions to familiarize them with the system. After two weeks, the patient will be issued an interACTION device for home use that will guide them through their exercise program. At this point subjects in the interACTION group should continue to return to the outpatient rehabilitation facility, but reduce their weekly routine visit with their physical therapist by one during the next eight weeks of recovery, while concurrently using interACTION at home. Patients who attended two visits per week for the first two weeks should subsequently attend one visit per week. Patients who attended three visits per week for the first two weeks will subsequently attend one to two visits per week. However, if the physical therapist feels it to be in the best interest of the patient to deviate from the protocol, this is allowed.

*Note: InterACTION is currently under development, not a commercial application. The 3rd Party Developer was OpenArc, LLC ([name]). The mobile application is currently supported on a Nexus tablet with Android operating system (specifically lollipop and kitkat versions). The mobile application and the kinematic sensors will be provided to the participant, the participants will NOT use a personal device.*

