Rehabilitation Compliance will be evaluated by the study team through the use of home exercise logs and interACTION reports. Logs will be reviewed at the follow-up visits with the research team. Outcome measures will be collected at baseline, 5 weeks (+/- 7 days) after enrollment, and upon discharge or a maximum of 10 weeks (+/- 7 days) after enrollment.

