### *Outcomes*

- Range of motion—Active and passive range of motion (ROM) will be measured with a standard goniometer while the patient lies in the supine position. Extension and flexion of each knee will be measured. Extension will be measured passively with a quad set and actively during a straight leg raise. The range of extension and flexion will be expressed as the difference between the involved and non-involved knees.
- Numeric Pain Rating Scale—Subjects will be asked to rate their level of pain currently and their level of worst & least pain in the past 24 hours on a scale from 0 (no pain) to 10 (worst pain imaginable).
- Activities of Daily Living Scale of the Knee Outcome Survey (ADLS)—The ADLS is a 14-item measure of symptoms and activity limitations for

individuals with a variety of knee impairments.

- Veterans RAND 12-Item Health Survey (VR-12)—The VR-12 is a 12-item patient-reported general measure of health-related quality of life that was adapted and developed from the RAND 36-Item Health Survey at the RAND Corporation and Medical Outcomes Study.
- Functional performance will also be tested in all patients. The following functional tests will be assessed at 5- and 10-week visits:
  - Six-minute Walk Test to assesses the subject's ability to walk community distances. The subject is asked to walk as far as possible in six minutes on a closed course with standing rest breaks as needed. The patient is free to use their preferred assistive device.
  - The Stair Climbing Test to test basic daily function in which a patient ascends and descends a standard flight of stairs as quickly and safely as possible, using their preferred gait pattern, assistive device, and hand rail.
  - The Timed Up and Go Test (TUG) in which the patient sits in a standard armed chair, rises, walks three meters, turns around, walks back to the chair and sits. Excessive time to complete the TUG can indicate mobility impairments and potential fall risks in elderly patients.
  - The Unilateral Balance Test in which the patient attempts to maintain single leg balance for up to two minutes, with the test ending when the patient loses balance enough to put the opposite foot on the ground.

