#### *Statistical Analysis*

For the baseline data, continuous variables were compared with the two-sample t-test and categorical variables were compared with Fisher's exact test or a chi-square test.

For the primary outcome (value, ratio of ADLS to cost), the Wilcoxon rank sum test was used to compare between the Control Group and interACTION Group. P-Values below \* $p=0.05$  were considered statistically significant for all outcomes. For the remainder of the cost analyses parameters (weeks of physical therapy, number of physical therapy visits, and total cost), a two-sample t-test was used to compare between groups.

For other clinical outcomes data, if the distribution was normal at each time point, then a repeated measures ANOVA was used. A repeated measures ANOVA was used to compare difference between groups for the ADLS, Passive ROM (flexion), and Active ROM (flexion). Otherwise, if some time points had normal data and others did not then a two-sample t-test was used for normally distributed data and the Wilcoxon rank sum test was used for non-normally distributed data.

For the functional performance tests that were assessed at the 5- and 10-week visits, a z-score (or standard score) was used to calculate a cumulative score for the Six-minute Walk Test (distance in feet), Stair Climb Test (time divided by steps), TUG (time), and Surgical Unilateral Balance (time). The z scores are the average of the z scores for each of the functional tasks. On average, the z scores are close to zero, meaning that the overall individuals within the group, the scores for each subject are not different than the mean score across all subjects.

Differences between the cumulative z-scores were assessed using a two-sample t-test.

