#### *Inclusion criteria*

Males and females between 40 and 80 years of age that have undergone primary unilateral TKA who have been referred for post-operative outpatient physical therapy will be eligible to participate in this study. Additionally, eligible subjects also need to be able to perform pre-defined exercises that they would normally

perform in a physical rehabilitation program.

The Physical therapists that will be asked to complete the Clinician Survey must have a patient participating in the study to be considered eligible.

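### ROM is defined as a side-to-side difference and analysed without baseline covariates; involved-knee ROM adjusted for both knees' baseline would be expected to be more precise, though not at every correlation

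*Combined protocol and SAP*

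**What the plan says.** Under Outcomes, the plan provides that "Extension and flexion of each knee will be measured", and then that "The range of extension and flexion will be expressed as the difference between the involved and non-involved knees". The Methods section schedules a baseline assessment: "Outcome measures will be collected at baseline, 5 weeks (+/- 7 days) after enrollment", with a last assessment at discharge or 10 weeks at most. So ROM of both knees should be available before and after the intervention.

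The Statistical Analysis section states: "A repeated measures ANOVA was used to compare difference between groups for the ADLS, Passive ROM (flexion), and Active ROM (flexion". If some time points are not normally distributed, it moves to a t-test or a Wilcoxon rank sum test, visit by visit. None of these carries a covariate. The section does not say which ROM value enters the analysis or which ANOVA term is the treatment test.

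Eligible patients "have undergone primary unilateral TKA", so the other knee serves as a reference. Nothing in the inclusion criteria requires that knee to be healthy. The exclusion criteria remove comorbidity that would hinder the exercises, which limits badly impaired other knees but does not rule out a stiff, usable one. ROM is not the primary outcome; that is the ratio of ADLS to cost.

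**The concern.** A difference between knees makes the other knee part of the outcome with a weight of exactly 1. If the knees are only moderately correlated, much of what is subtracted is the other knee's own variation and goniometer error, which say nothing about the effect of the programme. A small difference can also mean a good operated knee or a poor reference knee.

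With 30 patients per arm, avoidable variance matters when the question is whether motion is preserved with fewer clinic visits. The plan collects baseline ROM on both knees but names no use of it as a covariate.

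**Working it through.** **Inputs.** From the documents: 60 patients, 30 per arm; both knees measured; a baseline visit. The documents give no ROM SD, no between-knee correlation and no sample-size basis, so there is no planned figure to reproduce. Everything below is assumed and shown as a range. Set the involved knee's SD to 1. Let k be the other knee's SD, rho the same-visit correlation between knees, s the other knee's correlation between visits (stability), and a the involved knee's correlation between baseline and follow-up. The plan's difference is read as using both knees at the same visit.

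**Step 1. Same measurement, subtracted or fitted, at one visit.**
- Difference: 1 + k² − 2·rho·k
- Fitted covariate: 1 − rho²
- Excess from subtraction: (k − rho)², never negative

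| rho | k = 1: difference / fitted | ratio | k = 0.7: difference / fitted | ratio |
|---|---|---|---|---|
| 0.2 | 1.60 / 0.96 | 1.67 | 1.21 / 0.96 | 1.26 |
| 0.5 | 1.00 / 0.75 | 1.33 | 0.79 / 0.75 | 1.05 |
| 0.7 | 0.60 / 0.51 | 1.18 | 0.51 / 0.51 | 1.00 |

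At N = 60, estimating one slope multiplies the fitted variance by 1 + 1/56 = 1.018, so the fitted version can lose very slightly when rho is close to k. Simulation with 30 per arm at k = 1, rho = 0.5 gave 1.007 against 0.76, in line with theory.

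**Step 2. Subtraction against the involved knee alone.** Subtraction raises variance only if 1 + k² − 2·rho·k > 1, that is, rho < k/2. At equal SDs it is neutral at 0.5 and helps at 0.7 (0.60 against 1.00).

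**Step 3. Baseline value of the other knee as covariate.** A same-visit covariate is measured after randomisation and is safe only if treatment leaves that knee unaffected. The baseline value avoids this, but its correlation with follow-up involved-knee ROM is weaker, taken here as s·rho. The fitted variance becomes 1 − (s·rho)². Difference divided by fitted, k = 1:

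| rho | s = 0.9 | s = 0.8 |
|---|---|---|
| 0.2 | 1.60/0.968 = 1.65 | 1.60/0.974 = 1.64 |
| 0.5 | 1.00/0.798 = 1.25 | 1.00/0.840 = 1.19 |
| 0.7 | 0.60/0.603 = 0.99 | 0.60/0.686 = 0.87 |

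Below 1 the same-visit difference is the more precise. The crossover is rho = (1 − √(1 − s²))/s², which is 0.70 at s = 0.9 and 0.625 at s = 0.8. It comes earlier when k is smaller: at k = 0.7, s = 0.9, rho = 0.5 the ratio is 0.79/0.798 = 0.99.

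**Step 4. Group-by-time contrast.** The stable part of the other knee cancels in a change score. The other knee's own change has variance 2k²(1 − s): 0.2 at s = 0.9 and 0.4 at s = 0.8 for k = 1, against 1 at a single visit.

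**Step 5. Adjustment for both baselines.** The variance of follow-up involved-knee ROM is 1 − [a² + (s·rho)² − 2·a·s·rho²]/(1 − rho²), times 1 + 2/55 = 1.036 for two slopes. The change in the difference has variance 2(1 − a) + 2k²(1 − s) − 4k·rho(1 − s). Two examples at k = 1, a = 0.5:
- rho = 0.5, s = 0.9: adjusted 0.697 × 1.036 = 0.722; single-visit difference 1.00 (ratio 1.39); change in difference 1.00 (ratio 1.39). The change in the involved knee alone is also 2(1 − 0.5) = 1.00, so the gain over the change score comes from baseline adjustment, not from dropping subtraction.
- rho = 0.8, s = 0.8: adjusted 0.590 × 1.036 = 0.611; single-visit difference 0.40 (ratio 0.65, a loss); change in difference 0.76 (ratio 1.24).

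Over rho 0.2 to 0.8, k 0.7 and 1, s 0.8 and 0.9, a 0.3 and 0.5, the ratio against the change in difference was at least 1.17. Over a wider set of assumed correlations, adjustment for both baselines beat the single-visit difference in about 76% of settings and the change in difference in about 94%, with median variance ratios of about 1.3 to 1.5. These are shares of assumed settings, not probabilities.

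**The case against.** The strongest objection is that the clean algebra and the practical remedy are different things. A reader might infer from Step 1 that covariate adjustment is as good or better at any correlation. That holds only when the same non-involved measurement is used both ways. Subtracting the same-visit value is not a special case of a model with the baseline value, so for the remedy both the size and the direction of the gain depend on correlations that the documents do not give. This objection stands, and the claim is limited accordingly.

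It is also fair that the planned test for flexion is a repeated measures ANOVA with a baseline visit. If the treatment test is the group-by-time term, subtraction costs much less than the single-visit figures suggest, and most of the gain may come from baseline adjustment. This stands too, but it supports the remedy, since baseline adjustment is part of it.

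A reader might further infer that the planned analysis is biased because some reference knees are poor. The documents do not support that. Patients are randomised, so poor other knees balance in expectation, and if treatment leaves that knee unaffected both approaches estimate the same treatment difference. Nor is ROM presented as a main outcome: it sits among the other clinical outcomes of a pilot study.

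Finally, the Statistical Analysis section is written in the past tense. If the analyses have already been run, a new ROM analysis is post hoc and must be labelled so.

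**Conclusion.** The point holds as an efficiency recommendation. The plan fixes the other knee's coefficient at 1, names no baseline covariate, and leaves open which ROM value is analysed. At a single visit with equal SDs, subtraction costs a variance ratio of 1.67, 1.33 or 1.18 at rho 0.2, 0.5 or 0.7 relative to fitting the same measurement. With k = 0.7 the ratios are 1.26, 1.05 and 1.00. The loss is smaller in a group-by-time contrast. For the remedy itself a gain is likely but not assured: it can lose to a same-visit difference when between-knee correlation is high and the other knee's ROM is unstable.

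A reader might take the 1.67 to mean that 60 patients carry the information of only 36 (60/1.67). That is the least favourable of the tabulated settings, for a single-visit comparison with a same-visit covariate, and does not describe the planned ANOVA. All SD ratios, correlations and stabilities are assumptions. Only precision on a non-primary outcome is affected.

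**What to change.** In the Statistical Analysis section, state that the analysed value is involved-knee ROM at 5 weeks and at the final visit (discharge, or 10 weeks at most), adjusted for baseline ROM of the involved knee and of the non-involved knee. Keep the side-to-side difference as a descriptive or supportive summary; if it is tested, use the same two baseline covariates. Name the model term that is the treatment comparison.

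No new data are needed, only wording if the analysis has not been run. If it has, report the adjusted analysis as post hoc beside the planned one. The downsides are small: up to two degrees of freedom (about 3.6% in variance at N = 60), a possible loss at high between-knee correlation, and no direct counterpart in the Wilcoxon fallback, for which the section should say what will be done.

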A web-accessible, password-protected portal allows a local or remote physical therapist to monitor the patient's progress. Physical therapists have access to the data to analyze patient progress and compliance and review computer-generated alerts. Capabilities in the clinician portal include assessment of patient data during exercises and activities of daily living (ADLs), weekly progress reports by reviewing changes in important variables (i.e. range of motion, pain, patient-reported activity, participation, quality of life). The ability to monitor progress ensures the patient's compliance to the treatment program and allows clinicians to update the patient's exercise regimen as needed.

Use of the interACTION system has the potential to allow physical therapists to improve patient-oriented outcomes, streamline utilization of clinical resources, and provide care more efficiently for a larger number of patients. In turn, patients will be more confident and compliant with performance of their prescribed exercise program and will receive feedback on their recovery progress. However, research is needed to demonstrate these hypothesized benefits of the interACTION system.

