Subjects will also undergo an interview to give a qualitative description of rehabilitation experience upon discharge from outpatient physical therapy or at the 10-week visit. This interview will entail an open-ended discussion with patients about their overall rehabilitation experiences, experiences with home exercises (either monitored or unmonitored), experiences with clinic-based workout sessions, and expenses incurred during the rehabilitation process.

Additionally, the physical therapists that are using the device with the study subjects will be interviewed to describe their experience with patient rehabilitation after surgery, and about their experience with the interACTION system.

The physical therapist will also be asked to complete the Clinician Survey, which will be administered by a research staff upon discharge of the patient, or a maximum of 10 weeks (+/- 7 days) after enrollment. All subjects participating in the study will be informed that their compliance will be evaluated by their physical therapist at this time of discharge, or a maximum of 10 weeks (+/- 7 days) after enrollment.

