#### *Potential Benefits*

This study aims to increase knowledge related to use of the interACTION device to supplement post-operative rehabilitation after TKA. If the interACTION device leads to improved post-operative outcomes, patients in the future would benefit from use of the device to supplement their post-operative rehabilitation program. If beneficial, use of the interACTION device would result lead to the same or better outcomes with fewer in-clinic physical therapy visits, thus improving the value of care with lowered healthcare costs and expenditures.

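### The cost in the primary outcome (ADLS divided by cost) is undefined, and no described data source captures the device or remote monitoring; a visit-based cost that omits them favours interACTION

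*Combined protocol and SAP*

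**What the plan says.** The Statistical Analysis section fixes the endpoint: "For the primary outcome (value, ratio of ADLS to cost), the Wilcoxon rank sum test was used to compare between the Control Group and interACTION" arms. It then sends three further quantities to a t-test: "For the remainder of the cost analyses parameters (weeks of physical therapy, number of physical therapy visits, and total cost". It does not say what total cost contains, whose cost it is, how a visit is priced or where the data come from.

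The Abstract announces a cost comparison, but the Outcomes list has no cost item. Expenses appear once, as one topic of the patient interview at the end of the course: "experiences with clinic-based workout sessions, and expenses incurred during the rehabilitation process". The purpose given for that interview is descriptive: "Subjects will also undergo an interview to give a qualitative description of rehabilitation experience upon discharge from outpatient physical therapy or at the 10-week visit".

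The intervention uses two resources that the control arm does not. The Methods note says of the equipment: "The mobile application and the kinematic sensors will be provided to the participant". The Background says of the clinician portal: "Physical therapists have access to the data to analyze patient progress and compliance and review computer-generated alerts". The Risks section also mentions online review by the therapist. Neither resource is priced, and the therapist's time is not said to be recorded.

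The conclusion sought concerns healthcare cost. The Significance paragraph of the Abstract looks to lower healthcare spending, and Potential Benefits expects fewer visits with equal or better outcomes, "thus improving the value of care with lowered healthcare costs and expenditures".

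**The concern.** Cost is half of the primary endpoint, so its definition decides what a positive result means. The protocol reduces clinic visits in one arm only and replaces part of them with a device and remote supervision. A fair value comparison has to count both the visits removed and the resources added.

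The described data would show the first but not the second. Visits and weeks of therapy cannot contain a device or portal charge. A patient asked about expenses would not be expected to report equipment that the study supplied, or therapist time spent out of sight. Billing records may not contain the device either, because the Methods note describes interACTION as still in development and not commercially sold. Leaving these items out is therefore the likely default unless a rule says otherwise. A significant primary result could then reflect uncounted cost rather than better value, and the analysis could not tell the two apart.

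**Working it through.** The documents state no cost figure, so there is none to reproduce. The check asks how far the primary ratio could depend on the unstated costing rule.

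**Inputs from Methods.** Control: two to three visits per week for up to ten weeks. interACTION: two to three per week for two weeks, then eight weeks at a reduced rate. Two-per-week starters go to one. Three-per-week starters go to one or two, although the same section also speaks of a reduction by one. Both permitted schedules are calculated here.

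**Assumptions.** Equal ADLS in the two arms, cost proportional to visits, and a full ten-week course. Let x be the device and monitoring cost per interACTION patient, in visit-equivalents. No document gives x.

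**Formula.** interACTION value divided by control value = control visits / (interACTION visits + x). Break-even x = control visits − interACTION visits.

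| Visits per week | Control | interACTION | x = 0 | x = 4 | x = 8 | Break-even x |
|---|---|---|---|---|---|---|
| 2, then 1 | 2×10 = 20 | 2×2 + 1×8 = 12 | 20/12 = 1.67 | 20/16 = 1.25 | 20/20 = 1.00 | 8 |
| 3, then 2 | 3×10 = 30 | 3×2 + 2×8 = 22 | 30/22 = 1.36 | 30/26 = 1.15 | 30/30 = 1.00 | 8 |
| 3, then 1 | 3×10 = 30 | 3×2 + 1×8 = 14 | 30/14 = 2.14 | 30/18 = 1.67 | 30/22 = 1.36 | 16 |

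For scale, x = 4 is half a visit per home week and x = 8 is one visit per home week. Ten weeks is a maximum. With a one-visit cut the saving is (weeks − 2) visits, so a shorter course lowers the break-even. At six weeks, for example, a two-per-week starter has 12 versus 2×2 + 1×4 = 8 visits, a ratio of 1.50 and a break-even of 4.

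**Effect on the planned test.** An illustrative simulation of the Wilcoxon comparison used 2,000 runs with 30 patients per arm. It assumed ADLS of mean 75 and SD 12 in both arms, two or three visits per week equally likely, a one-visit cut, and courses of 6 to 10 weeks. Significance was two-sided at 0.05; the plan does not state sidedness.

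| x | Significant for interACTION | Significant for control |
|---|---|---|
| 0 | 97% | 0% |
| 2 | 73% | 0% |
| 4 | 20% | under 0.1% |
| 6 | 3% | 3% |
| 8 | under 0.1% | 25% |

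The crossover lies near x = 6 because the mean simulated course is 8 weeks, a mean saving of 8 − 2 = 6 visits. The percentages depend on these assumptions. What they show is that the direction of the primary result can turn on x alone.

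**If cost is recalled patient expense.** The formula no longer applies. Any insurer-paid part of a visit is then missing from both arms, and more of it from control, which has 8 to 16 more planned visits. If patient expense did not rise with visits and was equal in the arms, the ratio would be 1.00. Against 20/(12 + x), that is too low for interACTION when x is below 8 and too high when x is above 8. The direction is not determined.

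**The case against.** A reader might infer that the interview supplies the denominator, that device and monitoring costs are excluded, and that the primary ratio is therefore biased towards interACTION. The documents do not support that. Nothing links the interview to the ratio, and its stated purpose is qualitative. The Statistical Analysis section lists total cost beside visits and weeks, and a variable analysed by t-test needs a quantitative source, even though none is described. Because total cost is undefined, the device and the monitoring are neither included nor excluded. The one-sided direction is certain only for a visit-based cost that omits them.

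Further points stand. The values of x are hypothetical, and under the 30 versus 14 schedule interACTION keeps an advantage even at x = 8. Therapists are also interviewed and complete a Clinician Survey. The contents of these are not in the documents, so they might touch on monitoring burden, but they are not described as recording time or cost. The portal passage is a description of capabilities; no section sets how often or how long therapists review data. The study is a pilot of a non-commercial device, so any device charge will be an assumption.

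These points limit the claim to a conditional one. They do not supply the missing costing rule, and none identifies a source that would capture what the intervention adds.

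**Conclusion.** The point holds in conditional form. The denominator of the primary outcome has no stated components, perspective, unit prices or source, and no described data would capture two resources used only in the interACTION arm.

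If cost is visit-based and those resources are left out, any positive omitted amount favours interACTION. Under equal ADLS, visit-proportional cost and ten full weeks, the ratio starts at 1.36 to 2.14 before any clinical benefit, and it takes 8 to 16 visit-equivalents of omitted cost to cancel it. The actual omitted cost cannot be estimated from the documents, so bias in the primary result is not established. If cost is recalled patient expense, no direction can be claimed, and the quantity is not the healthcare cost named in the study's conclusions. On either reading, the plan as written cannot soundly support a claim of lower healthcare cost.

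**What to change.** Define cost for the primary ratio in the Statistical Analysis section and state the perspective. A workable rule:

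- For both arms, take attended visits from clinic or billing records and multiply by one fixed unit cost.
- For interACTION, add an assumed per-patient device and server charge, plus therapist portal time at the therapist's rate. Log the time if feasible. The section is written in the past tense, so prospective logging may no longer be possible; a fixed minutes-per-week assumption would then serve.
- Report the primary ratio across a range of these charges, including zero and the break-even value.
- Keep patient-reported expenses as a separate secondary outcome.

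The cost is small. Visit counts are already needed for the planned analysis, and the sensitivity range needs no new patient data. What is added is one device-price assumption, one portal-time record or assumption, and SAP wording. The drawbacks are that the added charges are assumptions, which is why a range is reported, and that the value advantage may become less favourable.
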